9.3.2.2.3 Breastfeeding/Lactation Outcomes

Both assessed via questionnaire administered between 0–6 weeks postpartum (see [Appendix A](#), 02.F. Outcome Delivery and Birth Interview Form):

- Proportion of women who breastfed (at all) in the first 6 weeks after delivery
- Among women who breastfed (in the first 6 weeks after delivery), the proportion who breastfed exclusively during the first 2 weeks of life

9.3.3 Covariate Assessment

9.3.3.1 Maternal Intake Form

(At enrollment) Variables collected include demographic and socioeconomic information (occupation, education, race, ethnicity, income); pregnancy history; pre-pregnancy weight and height; family history; medical history (including history of onset and other characteristics of indications for evolocumab use); cholesterol test results prior to and during pregnancy (see [Appendix A](#), 02.B1. Demog Med Hist Interview Form and 02.B2. Cholesterol Study Form).

9.3.3.2 Exposure Interview Form

(At scheduled time points during pregnancy and post-delivery) Variables collected include current medication use (prescription and OTC); environmental and occupational exposures; alcohol, tobacco, caffeine, illicit drug use; current pregnancy complications; contact information of health care providers (see [Appendix A](#), 02.C. Exposure Interview Form).

9.3.3.3 Pregnancy and Delivery Outcome Interview

(Upon pregnancy ending) Data collected on this form include details regarding pregnancy and delivery such as maternal conditions, birth information, delivery details, and newborn complications (see [Appendix A](#), 02.F. Outcome Delivery and Birth Interview Form).

9.3.4 Validity and Reliability

For the primary exposure variable regarding evolocumab, maternal report will be confirmed by medical records abstraction. In cases of discrepancy, the mother will be queried to help resolve. For the primary outcome variable of major **structural** birth defects, maternal report is validated through medical record review and expert study investigator classification; external validation is performed by consultants and the Advisory Board as described above. For other outcome variables, standard methods are used to classify the outcome, and data management procedures are in place to confirm reliability of data capture, data entry and classification. The neurobehavioral testing instruments that have been selected for this study have been validated in the age groups for which they will be used. Reliability procedures are in place for test administration and scoring and are overseen by the study psychologist.

9.4 Data Sources

Standard study interview and data collection forms are listed in [Appendix A](#) and summarized below.

9.4.1 Initial Intake Interview

Upon enrollment, **subjects** will be interviewed using the Maternal Intake Form (see [Appendix A](#), 02.B. Personal Information Interview Form, 02.B1. Demog Med Hist Interview Form, 02.B2. Cholesterol Study Form, and 02.C. Exposure Interview Form) the purposes of which are to collect information on demographic and socioeconomic characteristics, pregnancy history, family history, and medical history.

9.4.2 Interim Interviews

Following the initial intake interview, **subjects** will be sent a pregnancy diary in which they will be asked to record any additional exposures or events as the pregnancy progresses (see [Appendix A](#), 03.D. Patient Exposure Diary), **as well as the obstetric medical record release form.**

A subject may have 1 to 3 interviews during pregnancy, with a minimum of 4 weeks between interviews. If a subject enrolls at 18 weeks, the 20-week interview will be scheduled at 22 weeks. If a subject enrolls between 19 weeks and < 30 weeks, the next scheduled interview will be at 32 weeks. If a subject enrolls at 30 weeks, the 32-week interview will be scheduled at 34 weeks. If a subject enrolls after 30 weeks, no additional interviews will be scheduled during pregnancy (see [Table 1](#), and [Appendix A](#), 02.C. Exposure Interview Form and 02.F. Outcome Delivery and Birth Interview Form). The purpose of these interviews will be to update records of pregnancy exposures and results of prenatal tests, to remind women to maintain the exposure diary, to update phone number and address information, and to determine if the pregnancy has ended prior to the expected due date.

9.4.3 Outcome Interview

At any of the interim interview points, if the pregnancy has ended, the outcome interview will be conducted at this time or at the earliest convenient time for the mother (see [Appendix A](#), 05.G. Adverse Outcome Delivery and Birth Form or 02.F. Outcome Delivery and Birth Interview Form). For women who are still pregnant at the 32-34 week interview, the outcome interview will be conducted within 0 to 6 weeks after the expected due date (see [Appendix A](#), 02.F. Outcome Delivery and Birth Interview Form).

The outcome interview for live born infants will be a structured telephone interview and information will be elicited on the following: date of delivery, hospital location and mode of delivery; ethnicity, sex, birth weight, length and head circumference; Apgar scores; description of delivery or birth complications including malformations; type and length of hospital stay for mother and infant; delivering physician's and infant physician's names

and addresses; method of infant feeding; pregnancy weight gain; and additional exposures and results of prenatal tests occurring since the previous interview.

The outcome interview for spontaneous or elective abortions will also be structured and information will be elicited on the following: date and type of outcome; hospital location if applicable; prenatal diagnosis; pathology results if available; and additional exposures and results of prenatal tests occurring since the previous interview. The outcome interview for stillborn infants will include all of the above plus information on sex, birth size, and autopsy results, if available.

9.4.4 Medical Records, Pediatric Evaluations

Upon completion of the outcome interview, each woman will be mailed a packet containing medical records release forms for the delivery hospital, obstetrician (**if the release form has not been received**), pediatrician, internist, cardiologist or other specialty physician if applicable (see [Appendix A](#), Form 09.J. Sample OB Medical Records Release Form). For women whose pregnancies have ended in spontaneous or elective abortion or stillbirth, records release forms will be mailed for the specialty physician's evaluation, if applicable, and if prenatal diagnosis, pathology or autopsy reports are available. Each woman will be asked to sign the forms and to return them along with the **patient** exposure diary. Specific information on maternal cholesterol levels obtained prior to and during pregnancy will be requested for women in the Evolocumab-Exposed group and Comparison Group I.

Upon receipt of the signed medical records release forms, a standard physical evaluation form (see [Appendix A](#), 06.H. Birth Info and Private Pediatrician Form) will be mailed to each pediatrician or other physician responsible for the care of each live born infant. This form includes information on infant size at the time of the latest examination and questions about postnatal complications and congenital anomalies. After delivery, at 1 year of age, and annually thereafter until the child's fifth birthday, a medical records release form for the pediatrician or health care provider caring for the child will be sent to the mother for signature. The signed form along with a standard questionnaire about infant/child growth, congenital malformations, serious infections (see [Appendix D](#) for list of conditions qualifying as serious infection), hospitalizations, and adverse reactions to vaccinations administered is sent to the health care provider (see [Appendix A](#), 07.I. Pediatric One Year Follow-up Form, and 08.I2. Vaccine Information Form).

9.4.5 Developmental Behavioral Assessments

9.4.5.1 Phase I – Maternal Questionnaires at Infant Age 16 Months to 17 Months 30 Days

The developmental behavioral assessments consist of mail-out questionnaires completed by all mothers/primary caregivers when the child is 16 months to 17 months 30 days of age. The measures are described in [Table 2](#).

All mothers or primary caregivers in each of the 3 study groups will be asked to complete questionnaires about the development of their child when the child is 16 months to 17 months 30 days of age. These scales include the Ages and Stages Questionnaire, the MacArthur-Bates Communicative Development Inventories (CDI), **and the Modified Checklist for Autism in Toddlers (MCHAT-R)** will be mailed when the child is 15 months of age and the mothers or primary caregiver will be asked to complete it when the child is between 16 months and 17 months 30 days of age. The mothers/primary caregivers will also complete 2 questionnaires about their own functioning, the Center for Epidemiological Studies Depression Inventory (**CES-D**), and the Parent Stress Index (**PSI**) Short Form. This will allow for the preliminary evaluation of the child's motor skill, general mental ability, language development, and social and emotional development. Interpretation of these data will be aided by an understanding of the mother's social and emotional adjustment and stress context. Although a window is provided to allow the mother to complete the questionnaires, scoring for these questionnaires is standardized to the month of age of the child so comparisons between groups will appropriately be age-adjusted.

9.4.5.2 Phase II – Face-to-Face Developmental Testing at 3.5-5.0 Years of Age

When the children are at least 3.5 years of age but not yet 5.0 years of age, a subset will then be evaluated through a single set of direct assessments completed in the **subject's/child's** home setting, as well as an age appropriate set of maternally completed questionnaires. Preference will be given to the assessment of children exposed prenatally for the longest durations and children in each of the comparison groups who are of similar age. Longer duration exposures should improve the ability to assess risks because brain development continues throughout prenatal development and may be vulnerable to drug exposure beyond the first trimester. Direct assessment will be conducted using the Wechsler Preschool and Primary Scale of Intelligence-IV (WPPSI-IV). This standardized (Z-score), norm-referenced measure provides an evaluation of the child's general mental ability, verbal and non-verbal abilities, as well as

processing speed. The mother or primary caregiver will complete 1 questionnaire about the child’s development, the Behavioral Assessment Scale for Children (BASC-III), and questionnaires about her own functioning, the **CES-D**, the **PSI**, and the **Edinburgh Postnatal Depression Scale (EDPS)**. These questionnaires will provide additional information about the child’s social and emotional development in the family context. Additionally, a direct evaluation of the mother or primary caregiver’s cognitive functioning will be made using the Wechsler Abbreviated Scale of Intelligence (WASI-II). Understanding the cognitive level of the mother will facilitate accuracy of interpretation of children’s scores and any group differences.

Face-to-face assessments will be made until a sample size of 40/group (cohorts 1-3) has been reached. At this sample size, statistical power (0.80) will allow confidence in judgments of group differences of SD in primary score endpoints.

Table 2. Postnatal Developmental Screening and Evaluation, Phase I (16 Months and 17 Months 30 Days of Age) & Phase II (3.5-5.0 Years)

Age	Measure	Description
16 months – 17 months 30 days	Ages and Stages Questionnaire (ASQ-3) (Squires, 2009)	Used to screen infants and young children for developmental delays during the first 5 years of age. Parents complete an illustrated 30-item questionnaire that covers 5 key developmental areas: communication, gross motor, fine motor, problem solving, and personal-social areas of functioning.
16 months – 17 months 30 days	The MacArthur-Bates Communicative Development Inventories (CDI) (Fenson, 2007)	Used to assess the development of expressive and receptive language abilities during 2 early age periods. The CDI Words and Gestures is used for children 8-16 months of age and the CDI Words and Sentences is used for children 16-30 months of age.
16 months – 17 months 30 days	Modified Checklist for Autism in Toddlers (MCHAT-R) (Robins et al. 2001)	Used to screen for autism spectrum disorders in toddlers over the age of 16 months.
3.5-5 years	Wechsler Preschool and Primary Scale of Intelligence-IV (WPPSI-IV) (Wechsler and Psychological Corporation, 1989)	Provides an evaluation of the child’s general mental ability, verbal and non-verbal abilities, as well as processing speed. Completed via direct assessment.
3.5-5 years	Behavioral Assessment Scale for Children (BASC-III) (Reynolds and Kamphaus, 2004)	Completed by the mother or primary caregiver regarding the child’s development with respect to behavioral, emotional, and social characteristics.

Table 2. Postnatal Developmental Screening and Evaluation, Phase I (16 Months and 17 Months 30 Days of Age) & Phase II (3.5-5.0 Years)

Age	Measure	Description
16 months – 17 months 30 days and 3.5-5 years	The Center for Epidemiological Studies Depression Inventory (CES-D) (available through public domain; National Institute of Mental Health [NIMH])	Evaluation of the caregiver: Used as a screening tool for depression in adults. The mother or primary caregiver completes this 20 item questionnaire with respect to her/his own status.
16 months – 17 months 30 days and 3.5-5 years	The Parent Stress Index (PSI) Short Form (Abidin, 2012)	Evaluation of the caregiver: Used for the identification of parenting and family characteristics that fail to promote normal development in children as well as to detect children with behavioral and emotional problems.
3.5-5 years	Wechsler Abbreviated Scale of Intelligence (WASI-II) (Wechsler and Psychological Corporation, 1999)	Done via direct evaluation of the mother or primary caregiver. Designed for ages 6 to 89 years, used to better understand the cognitive level of the mother/primary caregiver.
3.5-5 years	Edinburgh Postnatal Depression Scale (EPDS) (Cox et al, 1987)	Evaluation of the caregiver: Used as a screening tool for “perinatal” depression. The mother or primary caregiver completes this 10-item questionnaire with respect to her own status.

Page 2 of 2

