9.3 Variables

9.3.1 Exposure Assessment

The period defining exposure to evolocumab during pregnancy will be any number of days, at any dose, and at any time from the first day of the LMP up to and including the end of pregnancy. Pregnancy will be assessed via maternal report validated by medical records. If the date of the LMP is unclear, or if a first-trimester ultrasound has been done and the estimated date of conception is more than 1 week discrepant from the menstrual period calculation, the first-trimester ultrasound-derived date will be used to calculate a date for LMP and conception.

The period defining non-exposure to evolocumab during pregnancy will be any time within 90 days prior to the first day of the LMP.

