While it is anticipated that not all mothers will agree to this sub-study, a sample size of 60 in each group will be targeted, with preference given to recruiting exposed pregnancies that represent the distribution of length of exposure.

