9.7.2.5.2 Secondary Analysis

The following will comprise the secondary analyses:

1. Comparison of all secondary outcomes between the Specific Evolocumab-Exposed cohort and Comparison Group I
2. Comparison of the primary and all secondary outcomes between the Specific Evolocumab-Exposed cohort and Comparison Group II

The comparison of the prevalence of the total proportion of major structural **birth** defects between the Specific Evolocumab-Exposed cohort and Comparison Group II will be among all live births and, separately, among all pregnancies excluding those lost to follow-up. The comparison of the prevalence of ≥ 3 minor malformations between the Specific Evolocumab-Exposed cohort and each of the 2 comparison groups will be among children who receive the dysmorphological examination. The comparison of IgG-tetanus antibody status (test negative or indeterminate vs test positive) by group (Exposed, Comparison Group I, Comparison Group II) among those in the biological sample sub-study.

In each cohort we will separately calculate the proportion of all pregnancies ending in live birth, spontaneous abortion, stillbirth, elective termination, and lost to follow-up; crude comparisons will be made between cohorts.

The evaluation for a pattern of minor structural **birth** defects will be conducted using the following steps:

1. A comparison among groups of the proportion of infants with any 3 or more minor structural **birth** defects will be made without regard to pattern
2. Among infants with 3 or more minor **structural birth** defects, the Evolocumab-Exposed group will be examined for evidence of a specific pattern of 3 or more defects in any 2 or more children. If such a pattern is identified, Comparison Groups I and II will be evaluated for any evidence of the same pattern.

In each cohort among all live born infants we will separately calculate the proportion of premature delivery, small for gestational age on weight, length or head circumference, and rates of serious infections, hospitalizations, adverse vaccine reactions, and adverse neurodevelopmental outcomes; crude comparisons will be made between cohorts.

Mean birth weight, length and head circumference for full-term live born infants will be compared between cohorts. Postnatal growth parameters will be compared using the proportion of infants ≤ 10 th centile for sex and age with respect to weight, height, or head circumference.

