9.9 Limitations of the Research Methods

The primary limitation of a cohort study utilizing volunteer subjects is selection bias. The use of comparably selected comparison women will address this concern to some extent, and support internal validity of the results. The use of a volunteer sample may not be representative of the entire population of evolocumab-exposed pregnancies. However, use of a disease-matched comparison group will allow for internal validity of comparisons.

It is likely that women prescribed evolocumab will be more severely diseased than the women in Comparison Group I (disease-matched control group), leading to confounding by indication. In addition, subjects in the Evolocumab-Exposed group are more likely to be exposed to additional medications to lower their LDL-C levels (including multiple medications and higher doses). Confounding by indication may also vary over time with increased awareness and access to the drug. In order to attempt to mitigate biases associated with confounding by indication, the Registry proposes to collect careful measurements of comorbidities including maternal cholesterol levels and comorbidities including cardiovascular disease history that are likely to differ across cohorts. Additionally, methods such as propensity scores may be utilized in attempts to balance covariates between comparison groups. Nonetheless, unmeasured confounding remains a limitation of the observational study design and should be recognized when interpreting results.

It is unknown to what extent women who agree to enroll in the cohort study may represent particularly high or low risk pregnancies. However, the study results will be strictly applicable to women fitting the profile of the sample of women who enroll.

The overall sample size is expected to be modest and limits the statistical power to detect differences on the primary and secondary endpoints. However, given the necessity and value of the study questions, we will capitalize on getting the most complete data possible regardless of the expected low frequency of pregnancy exposure to evolocumab.

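### Phase II ranks exposed children by total length of exposure, which is capped by gestation, so it can under-represent preterm children in the exposed group only; a cheap rewording removes this

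*Protocol*

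**What the plan says.** Section 9.4.5.2 tests a subset of children face to face: "Face-to-face assessments will be made until a sample size of 40/group (cohorts 1-3) has been reached". The rule for choosing them is: "Preference will be given to the assessment of children exposed prenatally for the longest durations and children in each of the comparison groups". For the two comparison cohorts the full condition is "children in each of the comparison groups who are of similar age". Gestational age at birth is not mentioned. The reason given is enrichment: "Longer duration exposures should improve the ability to assess risks because brain development continues throughout prenatal development".

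Section 9.3.1 defines the exposure window as any number of days, "at any time from the first day of the LMP up to and including the end of pregnancy". Section 9.5 expects 60 live births in the exposed cohort and 120 in each comparison cohort. Section 9.2.2 keeps recruitment open for ten years even if the exposed target is met earlier, while Phase II stays at 40 per group.

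For analysis, Section 9.7.2.5.2 plans for "adverse neurodevelopmental outcomes; crude comparisons will be made between cohorts", and later in the same section also plans adjusted estimates by regression, with propensity scores to be considered.

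**The concern.** Total exposure cannot be longer than the pregnancy. Among women who continue to delivery, ranking on total exposure is ranking on gestation, and the earliest births come last. Nothing comparable happens to the comparison children, who are chosen on age alone.

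One route by which a drug could affect neurodevelopment is earlier birth. If the exposed children born early tend to be the ones not tested, that part of any harm is thinned out of the exposed sample while the comparison sample keeps its usual preterm share. Taken alone, this favours the exposed group's scores. In a safety registry, that is the direction in which harm is missed.

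**Working it through.** **The plan's own figure.** Table 3 gives 80% power for 0.5 SD with 40 v 40. Two-sided at 0.05, z = 0.5/sqrt(2/40) - 1.96 = 2.236 - 1.960 = 0.276, which is about 61% power. The smallest difference detectable with 80% power is about 0.63 SD. This is a separate matter and the point does not rest on it, but it gives the scale for the shifts below.

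**Inputs from the protocol.** 40 tested per group (9.4.5.2); 60 exposed live births (9.5); preterm baseline 9% and relative risk 2.8 (Table 3), so 0.09 x 2.8 = 0.252; target 0.5 SD (Table 3). A pool of 46, the exposed number that Table 3 uses for postnatal growth, serves as an illustrative smaller pool.

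**Assumptions, not in the protocol.** Gestation uniform over 30-37 weeks if preterm and 37-41 if term; women who do not continue have 4-13 weeks of exposure; the pool is complete and strictly ranked; preterm birth costs 0.5 SD on the score (range 0.3-0.7).

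**When the rule bites.** Only when more than 40 exposed children were exposed to delivery: above 40/60 = 67% of a pool of 60, or 40/46 = 87% of a pool of 46. Chance variation in the number continuing blurs these thresholds a little.

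**Simulated preterm share among the 40 tested exposed children:**

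| Share continuing to delivery | Pool 60, true 25% | Pool 60, true 9% | Pool 46, true 25% |
|---|---|---|---|
| 50% | 25% | 9% | 25% |
| 75% | 16% | 2% | 25% |
| 80% | 11% | 1% | 25% |
| 90% | 3% | 0% | 22% |
| 100% | 0% | 0% | 14% |

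If enrolment runs beyond plan the effect grows. With an illustrative 80 exposed live births and two-thirds continuing, the tested share is below 5% against a true 25%.

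**Shift in the mean score** = (true share - tested share) x cost of preterm birth.
- All continue, true 25%: 0.252 x 0.5 = 0.13 SD (0.252 x 0.3 = 0.08; 0.252 x 0.7 = 0.18).
- 75% continue, true 25%: (0.252 - 0.159) x 0.5 = 0.05 SD (0.03 to 0.07).
- All continue, no effect on preterm birth: 0.09 x 0.5 = 0.045 SD.

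**Check of the remedy.** Counting exposure only up to week 30, which every simulated birth reaches, with random ties, brings the tested preterm share back to 25% in every 25% scenario. The share of continuers among those tested is unchanged (99.7% under both rules with 75% continuing in a pool of 60). A cap at week 32, which some simulated births do not reach, restores it only to 21% at 75% continuing and 19% at 100%. The cap must therefore sit where nearly all live births pass it.

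**The case against.** Several objections stand and limit the point.

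- The gestation effect needs high continuation. Section 9.7.2.6 aims the primary endpoint at first-trimester exposure and treats later exposure as conditional. That sentence concerns birth defects, though, and Section 9.4.5.2 justifies its rule by exposure after the first trimester.
- Preference is not exclusion, and children reach the test age over many years. Strict ranking of a complete pool is a worst case.
- Enriching for long exposure is a legitimate choice. It changes which children the estimate describes and is not in itself an error.
- Harm through early birth would not vanish from the study: Phase I questionnaires go to all mothers in the three groups, and preterm delivery is its own secondary outcome.

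A reader might infer more than the protocol supports in four ways.

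- *That the comparison will only be crude.* Adjusted estimates are also planned. They do not solve this problem, because untested preterm children cannot be recovered, and adjusting for gestational age may remove the very pathway of interest.
- *That the longest-exposed women are the sickest by the protocol's own account.* Section 9.9 says: "It is likely that women prescribed evolocumab will be more severely diseased than the women in Comparison Group I". That compares users with non-users and is silent on severity by duration among users. Selection on severity is an inference. If it did occur it would probably push the other way, so the net sign is unknown.
- *That the protocol contradicts itself,* because the immune sub-study in Section 9.4.7 recruits "with preference given to recruiting exposed pregnancies that represent the distribution of length of exposure". That is a different endpoint with a different rule. Adopting it here would trade away the enrichment.
- *That Comparison Group I must be chosen by indication.* It already consists of women with ASCVD or FH, and Section 9.1 describes frequency matching by indication.

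**Conclusion.** The point holds as a conditional weakness in the sampling rule that is cheap to improve. The text treats exposed and comparison children differently, and total duration is bounded by gestation. The rule can therefore under-represent preterm exposed children and can bias the Phase II comparison; the protocol does not show that it will. The shift is at most about 0.13 SD (0.08 to 0.18) with a 25% preterm rate, full continuation, a pool of 60, strict ranking and the assumed preterm cost. It is about 0.05 SD at 75% continuing and nil at half or fewer. In a pool of 46 there is little distortion unless 90% or more continue. The change is still worth making because the selection cannot be undone in analysis and grows if enrolment exceeds plan.

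**What to change.** In Section 9.4.5.2, rank exposed children by weeks of exposure counted only up to a fixed gestational week that nearly all live births reach, and break ties at random. Add a sentence that the Phase II estimate refers to longer-exposed children and not to all exposed children. Settle this before Phase II children are selected.

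The cost is protocol wording, with no extra children or visits. The enrichment for exposure beyond the first trimester is kept. The one downside is that some tested children will have a slightly shorter total exposure than under the present rule.
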